2.1 Study theoretical basis

The incidence of esophageal cancer in China ranks the first in the world, and its incidence and mortality account for more than half of the world^[1]. Esophageal cancer is mainly divided into carcinoma (ESCC) and adenocarcinoma (EAC) according to pathological type, of which ESCC is the main histological type, accounting for 80% of esophageal cancer cases worldwide^[2]. The incidence of ESCC is high in certain ethnic groups and certain regions, and is affected by environmental factors (drinking and smoking) and genetic factors (mutations in enzymes that metabolize alcohol)^[3]. The 5-year survival rate of ESCC is only 15%-25%. China is a country with a high incidence of esophageal cancer and the main pathological type is carcinoma, accounting for 53.7% of the world's cases^[4], of which about 70% are patients over 60 years old^[5]. It is expected that with the aging of the population, the incidence of esophageal cancer in the elderly will further increase.

The best treatment for locally advanced esophageal cancer is centered on radical esophagectomy. However, for some esophageal cancer patients who are not suitable for surgical treatment (such as tumor location, tumor invasion degree, age, patient's own condition, patient's willingness for treatment), concurrent chemoradiotherapy is the main treatment option.

Elderly patients are often unable to receive surgical treatment or even concurrent chemoradiotherapy due to their pre-existing medical conditions, organ dysfunction, and poor physical condition. Therefore, the prognosis of elderly patients with advanced esophageal cancer is poor. The clinical treatment of this disease is difficult, and the cure rate is low, and the recurrence, metastasis, and mortality rates are high. Therefore, it poses a serious threat to the physical and mental health and life safety of elderly patients^[6]. Over the past 10 years, both domestic and foreign researchers have been exploring potential therapeutic targets for elderly patients with advanced esophageal cancer, but compared with other gastrointestinal tumors, research and development has lagged behind. At present, there is an urgent need to explore a new treatment model to improve the efficacy and improve the long-term survival and

quality of life of elderly patients.

2.2 Background

EGFR is an important prognostic factor and therapeutic target for esophageal cancer. EGFR overexpression accounts for 42.5%-85.7% of ESCC and is closely associated with high recurrence and low survival^{[7][8]}. Therefore, EGFR signaling molecules are regarded as biomarkers at various stages of the development of esophageal cancer^[9]^[10]. Monoclonal antibodies and tyrosine kinase inhibitors targeting EGFR have been developed to improve the survival rate of ESCC^[8].

Nimotuzumab is a new anti-EGFR monoclonal antibody jointly developed by Biotech Pharmaceutical Co., Ltd. and Cuba. The drug was launched in China in 2008 and has been approved for marketing in 30 countries around the world, and has been approved for esophageal cancer indications in 9 countries.

A real-world study from Cuba^[7] evaluated the efficacy of nimotuzumab combined with radiotherapy/chemotherapy/chemoradiotherapy in patients with locally advanced or metastatic esophageal cancer in Cuba. The study included 339 patients with locally advanced or metastatic esophageal cancer registered in the Cuban National Cancer Database between January 1, 2011 and January 1, 2015. The patients were matched by propensity score. Among them, 93 patients in the nimotuzumab group had received at least one nimotuzumab treatment, and 93 patients in the control group had not received nimotuzumab treatment. The results showed that the median OS of the nimotuzumab group was 11.9 months, which was significantly higher than that of the control group (6.5 months, $p = 0.004$); the 1-year and 2-year overall survival of the nimotuzumab group were 54.0% and 21.1%, while those of the control group were 21.9% and 0%, respectively (95% CI 0.24–0.74, $p = 0.004$). The risk of death in the nimotuzumab treatment group was 2.38 times lower than that in the control group. Another meta-analysis from China also conducted an meta-analysis of nimotuzumab combined with chemoradiotherapy for the treatment of esophageal cancer^[8]. The study showed that nimotuzumab can improve the treatment efficacy and prolong the

survival of patients with esophageal cancer without increasing the incidence of adverse events. Combined chemoradiotherapy/radiotherapy can be recommended for the treatment of patients with esophageal cancer. In 2019, Zhai Yirui et al. from the Cancer Hospital Chinese Academy of Medical Sciences published a study on nimotuzumab combined with chemoradiotherapy for the treatment of unresectable local advanced esophageal cancer ^[9]. The study included 26 newly diagnosed patients with esophageal cancer, with a median radiotherapy dose of 60 Gy, a median total nimotuzumab dose of 1200 mg, and an effective rate of 76.9%. The median follow-up was 30.5 months, and the median survival was 28.7 months. The 2-year and 3-year overall survival were 59.4% and 38.2%; the 2-year and 3-year progression-free survival were 51.4% and 33.3%. Another study conducted a retrospective analysis of the efficacy of nimotuzumab or cetuximab combined with chemoradiotherapy in the treatment of patients with locally advanced esophageal cancer ^[10]. The results showed that the ORR of the nimotuzumab + CRT group was 61%, slightly higher than that of the cetuximab + CRT group (43.5%), and the disease control rate of the nimotuzumab + CRT group was significantly higher than that of the cetuximab + CRT group ($P = 0.04$). Other survival analyses also showed that the median PFS of the nimotuzumab + CRT group was significantly longer than that of the cetuximab + CRT group (19.6 months vs 13.0 months, $p = 0.02$). The 1-year and 3-year OS of the nimotuzumab + CRT group were higher than those of the cetuximab + CRT group ($HR = 1.17$, $p = 0.23$).

At present, many studies have confirmed that nimotuzumab can improve the efficacy of esophageal cancer in the elderly. Common acute toxic reactions included esophagitis, pneumonia, leukopenia, gastrointestinal reactions, and thrombocytopenia. The incidence of Grade 3-4 adverse reactions was 17.4%, and no Grade 5 toxic reactions were observed. The median overall survival (OS) was 17 months, and the progression-free survival (PFS) was 10 months. The 2-, 3-, and 5-year OS and PFS were 30.4%, 21.7%, and 19.6%, and 26.1%, 19.6%, and 19.6%, respectively. This result confirms that nimotuzumab combined with radiotherapy is a safe and effective treatment for elderly patients who cannot undergo surgery. Li Lulu ^[11] randomly

divided 67 patients aged 60-80 years with locally advanced esophageal cancer into an experimental group and a control group. 34 patients in the study group were treated with nimotuzumab combined with IMRT, while 33 patients in the control group were treated with IMRT alone. The results showed that the short-term response rate (ORR) of the study group and the control group were 85.2% and 63.6%, respectively, and the disease control rate (DCR) was 97.1% and 81.8%, respectively, with significant differences ($P < 0.05$). Although the 1-, 2-, and 3-year survival rates of the study group were higher than those of the control group, the difference was not statistically significant ($P > 0.05$). The adverse events of the two groups were similar, with no significant difference ($P > 0.05$). Conclusion: nimotuzumab combined with IMRT can significantly improve the ORR and DCR of patients with locally advanced esophageal cancer in the elderly, but it does not significantly improve the 1-, 2-, and 3-year survival rates of patients. In addition, JINHUA GUO ^[12] retrospectively analyzed the clinical data of 16 elderly patients with esophageal squamous cell carcinoma, aged > 70 years, who were treated with nimotuzumab combined with RT. The treatment efficacy was evaluated at the completion of treatment and re-evaluated 1-2 months later: 1 patient achieved complete response (CR), 10 patients achieved partial response (PR), 4 patients showed stable disease and 1 patient developed progression disease and died of radiation pneumonitis (RP) 1 month later. The overall response rate (CR + PR) was 68.8%. All 16 patients developed Grade 1-2 radiation esophagitis; no Grade 3-4 toxicity was reported. There was 1 RP-related death during the study. One patient developed a rash on the forearm. No hematological, gastrointestinal, liver, or kidney toxicity was observed. In conclusion, nimotuzumab combined with radiotherapy has good efficacy, tolerable toxicity, and high safety in the treatment of elderly patients with esophageal cancer.

The above studies provide evidence support for the treatment of EGFR-positive elderly esophageal cancer with nimotuzumab combined with chemoradiotherapy. In order to further verify the effectiveness and safety of nimotuzumab combined with concurrent chemoradiotherapy in the treatment of elderly patients with locally advanced unresectable advanced esophageal cancer, we conducted an exploratory

study on the effectiveness and safety of nimotuzumab combined with concurrent chemoradiotherapy in the treatment of elderly patients with locally advanced unresectable esophageal cancer, in order to obtain more sufficient evidence of benefits based on elderly patients, and add new evidence for the treatment of elderly esophageal cancer with nimotuzumab combined with chemoradiotherapy.

2.3 Risk/benefit assessment

2.3.1. Known potential risks

●Direct risks: From January 1, 2009 to June 1, 2020, it is estimated that approximately 117,187 patients used nimotuzumab in China. The company collected 688 adverse events reported by 459 patients. The names of adverse events were classified and summarized according to the ICH International Medical Terminology Dictionary (MedDRA) system organ class and preferred terms as shown in the appendix. Among them, there were 334 serious adverse reactions (including 180 new and serious adverse reactions, with ≥ 2 occurrences of bone marrow suppression, decreased platelet count, decreased white blood cell count, dyspnea, decreased neutrophil count, shortness of breath, hypersensitivity, anaphylactic shock, pruritus, anorexia, infectious pneumonia, decreased white blood cell count, decreased neutrophil count, decreased granulocyte count, decreased pancytopenia, lung inflammation, hypertension, and hematopoiesis. All serious adverse reactions did not reach the level of death or life-threatening), and 354 general adverse events (including 70 new general adverse events). According to the results of completed clinical studies and the post-marketing adverse reaction monitoring, nimotuzumab has shown good tolerability. Most adverse events are grade I, and common adverse events include nausea, vomiting, headache, fever, decreased neutrophils and white blood cells, anemia, fatigue. For the above adverse events, certain preventive measures or symptomatic treatment are taken, and most patients can be relieved after conventional treatment or on their own.

Serious adverse events mainly included hypersensitivity reactions, leukocytopenia. Demographic factors, concomitant medications, and medication dosages had no significant effect on the incidence of adverse events.

● Long-term risk: Four groups of repeated-dose toxicity studies were conducted in rats: continuous administration for 14 days, the highest dose reached 57.14 mg/kg, no animal deaths and no systemic toxicity were observed, and the NOAEL was 50 mg/kg. Once a week for 4 consecutive weeks, the highest dose was 75 mg/kg, no animal deaths and treatment-related abnormalities were observed, C_{max} and AUC_{0-inf} increased with increasing doses, and there was no difference in toxic kinetic parameters between genders, and the NOAEL was 75 mg/kg/w. Three groups of repeated-dose toxicity studies were conducted in green monkeys, with continuous administration for 14 days, the highest dose was 11.4 mg/kg, or once a week for 26 consecutive weeks, the highest dose was 28.57 mg/kg, and no obvious toxicity was observed. Repeated-dose toxicity studies were conducted in cynomolgus monkeys, with once a week for 26 consecutive weeks, the highest dose was 50.00 mg/kg, and no obvious toxicity was observed. No increased clinical risks associated with long-term use of nimotuzumab have been observed in previous clinical studies.

2.3.2 Known potential benefits

● Direct potential benefits: nimotuzumab was launched in China in 2008 and has been approved for marketing in 30 countries around the world, and has been approved for esophageal cancer indications in 9 countries. Many studies have shown that nimotuzumab is effective for patients with esophageal cancer.

2.3.3 Assessment of potential risks and benefits

● The mortality rate of esophageal cancer ranks fifth among malignant tumors. The rate will be higher in elderly patients with esophageal cancer due to their

limited tolerance to treatment. A safe and effective treatment method is urgently needed to be added to the treatment plan for this population. Nimotuzumab, as a drug with proven efficacy and widely recognized safety, is expected to bring higher efficacy benefits to patients with minimal safety risks. In addition, this study will limit the population that may increase the safety risk of patients to avoid inclusion in high-risk populations. At the same time, the details of possible adverse reactions and their treatment plans will be clarified to further reduce the risk.

3. Study purpose and endpoint

Purpose	Endpoint
Main purpose	
Exploring the efficacy of nimotuzumab combined with concurrent chemoradiotherapy for elderly patients with esophageal cancer	Primary endpoint: progression-free survival (PFS) Secondary endpoints: objective response rate (ORR), disease control rate (DCR), local disease control rate (LDCR), overall survival (OS), 1-year OS/PFS, 2-year OS/PFS, and AE/SAE incidence.
Secondary purpose	

4. Study design

4.1 Overall design

We plan to conduct a single-arm, prospective, single-center phase II clinical study to explore the efficacy and safety of nimotuzumab combined with concurrent chemoradiotherapy for elderly patients with locally advanced esophageal cancer. The

enrolled patients will receive nimotuzumab combined with S-1 and radiotherapy. This study includes a screening period, a treatment period, an efficacy follow-up period, and a survival follow-up period.

4.1.1 Screening period

●Definition: within 3 weeks before drug administration

●Content:

- 1) Sign the informed consent form;
- 2) Screening;
- 3) Demographic characteristics;
- 4) History of present disease;
- 5) Past medical history;
- 6) Combined treatment;
- 7) Body surface area (BSA);
- 8) Physical examination
- 9) Vital signs;
- 10) ECOG performance status: see 12.1. ECOG performance status scoring standards;
- 11) Nutritional status: see 12.4. Nutritional risk screening form (NRS 2002);
- 12) Quality of life: see 12.5. Quality of life score (QoL) of cancer patients;
- 13) Charlson Comorbidity Index: see 12.6. Charlson Comorbidity Index scoring criteria and calculation method;
- 14) Initial tumor imaging assessment:
 - a.Oral and intravenous contrast-enhanced CT (neck + chest + abdomen, and pelvis if necessary) is preferred;
 - b.Optional items include intraesophageal ultrasound, bone scan, esophageal fiber endoscopy, esophageal barium meal, PET/CT, etc.
- 15) Electrocardiogram (12 leads);
- 16) Laboratory examination of blood samples (hematology and

biochemistry);

17) Pregnancy test (female subjects of childbearing age);

18) Adverse events were observed and recorded.

4.1.2 Treatment period

●Definition: First radiotherapy day W1D1 - last radiotherapy day W5D5

●Window period: treatment ± 2 days, imaging ± 7 days, pre-dose items -1 day.

●Content:

1)Before WxD1 administration

a.Body surface area (BSA);

b.Physical examination

c.Vital signs;

d.ECOG performance status score;

e.Blood samples and other laboratory evaluations (hematology and clinical chemistry);

f.Electrocardiogram (12 leads);

2)Administer nimotuzumab (see 6.1.2. Dosage and administration);

3)Administer Tegafur (see 6.1.2. Dosage and Administration);

4)Administer radiation therapy (see 6.1.2. Dosage and administration);

5)Observe and record adverse events;

6)Combined treatment;

7)Imaging examination: Review every 21 days after W1D1 (such as W1D22).

4.1.3 End of treatment visit

●Definition: visit at the end date of radiotherapy

●Window period: ± 3 days

●Content:

1) Physical examination and vital signs check (at the end of radiotherapy);

- 2) ECOG performance status;
- 3) QoL (assessed at the first two efficacy follow-ups);
- 4) Nutritional status;
- 5) Hematology and clinical biochemistry (at the end of radiotherapy);
- 6) 12-lead electrocardiogram (at the end of radiotherapy);
- 7) Observation and recording of adverse events (AEs occurring within 7 days after the end of radiotherapy and SAEs occurring within 30 days);
- 8) Blood samples and other laboratory evaluations (hematology and clinical chemistry) are required if there are previously unresolved abnormalities;
- 9) Combined treatment.

4.1.4 Efficacy follow-up period

- Definition: From the end date of radiotherapy (D29) to the PD date
- Frequency (except for special items): The first review is on the 28th day after completion (W9D5), and then every 12 weeks starting from W9D5 until disease progression, with a window period of ± 7 days.
- Content:
 - 1) Film degree exam;
 - 2) Observation and recording of adverse events (AEs occurring within 7 days after the end of radiotherapy and SAEs occurring within 30 days);
 - 3) Hematology, biochemistry, electrocardiogram (if there are previously unresolved abnormalities, blood samples and other laboratory evaluations are warranted);
 - 4) Combined treatment.

4.1.5 Survival follow-up period:

- Definition: From PD date to death/loss to follow-up
- Frequency: Once every 12 weeks, window period ± 7 days
- Content:

- 1.Understand and record the subject's survival status, cause of death and time (telephone follow-up is possible);
- 2.Combined treatment.

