3. Record the name, dosage, start and end time of combined medications and treatments, as well as the reasons for combined medications and treatments;

4. Adverse events that have occurred will be followed until they disappear, improve or stabilize and the investigators believe that no further follow-up is required, including AEs that occur within 7 days after the screening period and SAEs that occur within 30 days after the end of radiotherapy;

5. Patients will be followed up for survival every 12 weeks after PD, and can receive telephone visits, including patient survival status and tumor treatment status. The specific cause of death will be recorded in detail when it involves the following factors (primary tumor recurrence, bleeding, perforation, new lesions; recurrence or new metastatic lymph nodes within and outside the region, etc.);

6. During the efficacy follow-up period, evaluation was only performed during the first two follow-up visits.

2. Introduction

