8.2.4 Timing and frequency of adverse event assessment and follow-up

The occurrence of adverse events (AEs) or serious adverse events (SAEs) should be brought to the attention of the investigator during visits to the subject receiving

medical care or for review by the monitor. All adverse events that do not meet the criteria for serious adverse events will be recorded on the appropriate case report form (CRF), including local reactions and systemic reactions. Information to be collected includes description of the event, time of onset, clinician's assessment of severity (which should only be assessed by those with training and diagnostic authority), relationship to the investigational product, expected nature, and time to resolution/stabilization of the event. All adverse events occurring during the study must be recorded, regardless of whether they are related to the study intervention. All adverse events are followed up until reasonably resolved. The medical condition at the time of screening of the subject should be considered as baseline and not reported as an adverse event. However, if the subject's condition deteriorates at any time, it should be recorded as an adverse event. Changes in the severity of adverse events should be recorded to allow for an assessment of the duration of the event at each severity level. Intermittent adverse events require the time of onset and duration of each occurrence to be recorded.

From the signing of the informed consent form to 7 days (non-serious adverse events) or 30 days (serious adverse events) after the end of the trial, the investigator should record all events that need to be reported. At each visit, the researcher should ask about adverse events/serious adverse events that occurred after the last visit. Follow up the outcome information of the event until the adverse event is resolved or stabilized. All serious adverse events should be followed up until the event is resolved satisfactorily, or the investigator considers the event to be chronic, or the subject's condition is stable.

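### The AE/SAE recording window is contradictory, and under the radiotherapy anchor later-onset toxicity drops out of the safety endpoint

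*Protocol*

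**What the plan says.** The protocol describes the recording period in several places, and they do not agree.

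- **Section 4.1.3 (end of treatment visit):** "AEs occurring within 7 days after the end of radiotherapy and SAEs occurring within 30 days".
- **Section 4.1.4 (efficacy follow-up):** the same limits, "Observation and recording of adverse events (AEs occurring within 7 days after the end of radiotherapy and SAEs occurring within 30 days". The same section sets the visit timing: "The first review is on the 28th day after completion (W9D5", with a window of ±7 days, and then reviews every 12 weeks until progression.
- **Section 1.3, footnote 4 (attached to the adverse event row):** "including AEs that occur within 7 days after the screening period and SAEs that occur within 30 days after the end of radiotherapy". The serious-event limit matches 4.1.3 and 4.1.4, but the 7 days have a different anchor.
- **Section 1.3, schedule table:** the adverse event row is ticked in every column, including efficacy follow-up and survival follow-up.
- **Section 8.2.4 (the section on timing of AE assessment):** "All adverse events occurring during the study must be recorded, regardless of whether they are related to the study intervention"; "At each visit, the researcher should ask about adverse events/serious adverse events that occurred after the last visit"; and recording runs from consent to "7 days (non-serious adverse events) or 30 days (serious adverse events) after the end of the trial".

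Section 1.1 names AE/SAE incidence as a secondary endpoint, and safety is part of the study purpose.

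**The concern.** An incidence endpoint needs one definition of which events enter the numerator. Here the anchor is the end of radiotherapy, the screening period or the end of the trial, depending on the section. The two main readings differ by most of the follow-up period.

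The narrow reading is the one printed in the visit-level instructions, which staff are likely to have in hand at the follow-up visit. On that reading a patient can attend a scheduled review with a toxicity that began a week or more after radiotherapy, and it need not be recorded.

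The trial has a single arm, so no control group is subject to the same undercount. A SAP can define which recorded events are tabulated, but it cannot recover events that were never collected.

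**Working it through.** The protocol states no figure to reproduce here. The check is calendar arithmetic plus a side-by-side reading.

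**Inputs.** Radiotherapy runs from W1D1 to W5D5 (section 4.1.2). The first review is 28 days after completion, at W9D5, ±7 days, and then every 12 weeks (4.1.4). The limits are 7 and 30 days after radiotherapy (4.1.3, 4.1.4). Visits last 24 months per subject (1.1), taken as 730 days.

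**Study days, with W1D1 = day 1.**
- End of radiotherapy, W5D5: 4 × 7 + 5 = day 33.
- Non-serious capture closes: 33 + 7 = day 40.
- Serious capture closes: 33 + 30 = day 63.
- First review, W9D5: 8 × 7 + 5 = day 61 (= 33 + 28), allowed range 54 to 68.
- Second review: 61 + 84 = day 145, which is 145 − 33 = 112 days (16 weeks) after radiotherapy.

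**Gaps under the radiotherapy anchor.**
- Non-serious: 54 − 40 = 14 days to 68 − 40 = 28 days before the first review. If the review is set 28 ± 7 days after completion, this gap does not depend on the date radiotherapy ends.
- Serious: 63 − 61 = 2 days after the review's target date, and 68 − 63 = 5 days before its window closes.
- Share of the visit period covered, counted from W1D1: 40/730 = 5.5% (non-serious) and 63/730 = 8.6% (serious).

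**Sensitivity to the end date.** Section 4.1.4 also labels the end of radiotherapy D29, and section 1.1 allows up to 30 fractions, which would end at W6D5 = day 40. Over ends from day 29 to day 40 the shares are 36/730 to 47/730 = 4.9% to 6.4%, and 59/730 to 70/730 = 8.1% to 9.6%. The conclusion does not change.

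**The rules applied to example events (onset counted from the end of radiotherapy).**

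| Event | 4.1.3 and 4.1.4 | Footnote 4 | 8.2.4 |
|---|---|---|---|
| Non-serious, day 5 | in | outside the period named | in |
| Non-serious, day 20 | out | outside the period named | in |
| Serious, day 20 | in | in | in |
| Serious, day 60 | out | outside the period named | in |

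The second and fourth rows change status between 4.1.3/4.1.4 and 8.2.4.

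**Survival follow-up.** The schedule ticks adverse event assessment in this column and 8.2.4 asks for enquiry at each visit. The content list in 4.1.5 has survival status, cause and time of death, and combined treatment, but no adverse event item.

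**The case against.** The strongest reply is that 8.2.4 is the dedicated section on AE timing and already requires what is wanted: all events during the study, enquiry at every visit, and an end point tied to the trial. Section 4.3 links study completion to examinations no longer being needed or the last subject's last visit, not to radiotherapy. The schedule ticks support this. Footnote 4 can also be read as listing events to be followed to resolution rather than capping collection. This much stands: the narrow window is not the protocol's only rule, and it would be wrong to say flatly that events after day 7 or day 30 are not collected. It does not settle the matter, because 4.1.3 and 4.1.4 state the narrow limits at the visits concerned, footnote 4 repeats the 30-day serious limit, and no section is said to take precedence.

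A reader might also infer that the plan would miss a fatal pneumonitis like the one in the retrospective series of 16 elderly patients described in section 2.2, where one patient "developed progression disease and died of radiation pneumonitis (RP) 1 month later", and might scale this to 0.0625 × 50 = 3.1, or about 3 of 50 patients. The documents do not support that:

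- The series evaluated patients at completion and again 1 to 2 months later, and the text does not say which evaluation starts the month. The death could fall at about day 30 or at about days 60 to 90.
- No onset date is given. Under section 8.2.2 the cause of death is the serious event and death is its outcome, so onset decides whether it falls in the window. An event that began in the window is followed until it resolves or stabilises.
- One event in 16 is 6.25%, with an exact 95% interval (beta quantiles 0.025 of Beta(1, 16) and 0.975 of Beta(2, 15)) of 0.16% to 30.2%. It cannot carry a projection, least of all one that assumes every case falls outside the window.
- A death would not vanish. Death before progression is a PFS event (section 8.1.1), and cause of death is recorded in survival follow-up (4.1.5).

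**Conclusion.** The contradiction is firm and rests on the protocol's own text: three anchors for one recording window, and a secondary endpoint whose numerator changes with the section followed. It should be corrected.

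The consequence is conditional. If staff follow 4.1.3 and 4.1.4, non-serious events starting after day 7 and serious events starting after day 30 are left out, and AE/SAE incidence is undercounted. If they follow 8.2.4, it is not. The clearest loss under the narrow reading is non-fatal toxicity of later onset.

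The size of the undercount is not known. It depends on what share of toxicity starts beyond 7 or 30 days, and the documents give no such distribution. The calendar gaps assume radiotherapy ends at W5D5 and are robust to the other end dates the protocol allows.

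**What to change.** Reconcile the section 1.3 schedule row and its footnote 4, sections 4.1.3, 4.1.4 and 4.1.5, and section 8.2.4 to one anchor and one window, consistent with 8.2.4. The same sentence should appear, or be cross-referenced, in each place. AEs and SAEs should be recorded at the efficacy follow-up visits already scheduled, at least at W9D5 and at the first 12-week review (about day 145). Replace the screening-period anchor in footnote 4.

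Report events during and shortly after radiotherapy separately from later ones, with the dividing day stated in advance. The acute figures then remain comparable with reports that used a short window.

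The cost is more CRF entries at existing visits and somewhat higher reported AE rates. No visit or test is added.
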